#### III. Risks

Pediatric CIDP is a rare condition and disease course if often prolonged with relapse and remissions. The subject sample size is small and meaningful clinical/biochemical changes following an intervention in CIDP patient population takes months to years. In general, these limitations are true for the majority of rare pediatric neuromuscular conditions. Alternative approaches include comparing the study population with historical controls however well-done natural history studies in pediatric CIDP are missing. We also anticipate patient compliance challenges. The usage monitor on the nVNS device will allow us to account for that in the data analysis.

nVNS at the level of the neck in children has been used in multiple studies. Patients may experience irritation at the site of stimulation; however this typically subsides within 10-15 minutes post-stimulation. In addition, patients may experience soreness in the neck due to activation of muscles, which is expected to be temporary.

Rarely, EKG changes have been described with nVNS. The study design includes regular EKG checks and if any changes or abnormalities are noted, this will be deemed as serious adverse event (SAE) and lead to termination of device use in the study participants. A follow-up visit and EKG will be performed for these subjects and if EKG abnormalities persist, pediatric Cardiology evaluation will be requested.

#### **IV.** Potential Benefits

Reduction of systemic inflammation in CIDP patients will halt degradation of motor nerve conductions and improve functional outcomes such as hand grip strength/ disability scores. Furthermore, nVNS therapy may lead to significant cost reductions in treatment and life-long healthcare costs of CIDP patients. Benefits of nVNS to patients will also reduce the disease burden on the patient's family by easing the treatment process.

#### V. Inclusion and Exclusion Criteria

Inclusion criteria:

- 1. Diagnosis of CIDP based upon clinical/electrophysiological criteria
- 2. Patient should be on treatment for CIDP including IVIG and/ or steroids/ plasma exchange
- 3. 5-21 years of age

Exclusion criteria

- 1. Patients will be excluded from the study if they have inherited polyneuropathy, such as Charcot Tooth Marie disease.
- 2. Abnormal baseline EKG, heart disease, epilepsy, pregnancy, multiple sclerosis and diabetes mellitus.

#### VI. Informed Consent Process

All pediatric CIDP patients followed in neuromuscular clinic would be eligible for the study. Study coordinator or PI will approach and consent these patients and their parents. For subjects older than 6 years of age, assent will also be documented.

#### VII. Data Safety

Oversight of the progress and safety of the trial will be provided by the PI. [name] will act as the study monitor and will check the progress of study and patient safety at regular basis. He will be notified directly within 24 hours of any adverse event. He will also be checking the data collected every 8 weeks in order to stay on top of the data safety.

Adverse events are not anticipated, but any occurring will be documented and reported according to Emory IRB policies and procedures. Cumulative adverse events and study progress summary will be communicated to the IRB at the time of continuing review.

The PI will identify serious adverse events (SAE).

Serious adverse events will be reported to the Emory IRB within 48 hours by the PI via a written and email correspondence. A log of adverse events will be kept while the study is in progress and reported to Emory IRB study safety officer on quarterly basis.

All patient data will be kept on an encrypted hard drive with access only to the members listed in this application. Data will be de-identified by referring to patients through assigned ID numbers (CIDP#), data will be kept for the duration of the study until publications are complete. Once complete, data will be permanently destroyed by mechanically destroying the data storage devices and shredding any potential paper-based forms/data.

The principal investigator (PI) will perform and supervise all evaluations during the study period.

Trained personal (M.D.'s) will be present during the conduct of this study. In case of serious adverse event the subject will personally evaluated by the PI within 24 hours of occurrence. Adverse events and unanticipated events will be evaluated within five days of occurrence.

All data obtained during the study will be kept confidential with the study coordinator, and PI on the password protected Children's Healthcare of Atlanta (CHOA) network and research office at Scottish Rite Hospital

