#### **Hypotheses**

# We hypothesize that nVNS therapy can reduce systemic inflammation in CIPD patients, functionally halting degradation of motor nerve conduction and hand grip strength.

The specific aims of this proposal are to:

- 1. Quantify functional changes in motor nerve conduction studies, hand held grip strength, and Rash-built Overall Disability Scale (R-ODS) in CIDP patients receiving standard of care treatment and daily nVNS.
- 2. Characterize changes in serum cytokine profiles in patients receiving standard of care treatment and daily nVNS.

We anticipate observing a reduction in serum TNF- $\alpha$  levels after nVNS therapy, consistent with previously published clinical results. Serum cytokine levels will be statistically analyzed on a per patient basis, with each patient's baseline measurements used for comparison. will be used to determine statistically significant differences between subsequent serum cytokine profiles for the entire patient population and NCS metrics. Pearson's correlation coefficient will be used to understand the relationship between changes in serum cytokine levels and NCS metrics. Pearson's correlation coefficient will also be used to assess the relationship between number of therapy session (as reported by the patient) and serum cytokine levels.

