#### II. Summary of Procedures

All proposed studies will be conducted at Children's Healthcare of Atlanta (Atlanta, GA) for a total duration of 24 months. Local institution review board approval would be obtained prior to the study. The table below (Table 1) provides an overview of the timeline and specific tasks to be completed upon each visit. Baseline represents the initial visit after the patient has been screened and meets the inclusion criteria (EKG results may take 24-48 hrs and study participant will be advised to start the study intervention once confirmation of normal EKG is obtained) Patients will be scheduled to visit the clinic for follow up visits at the pre-set time points shown. A total of 15 subjects, from age 5 years to 21 years, will be included in the study. The stimulation devices used in this study are VitalStim 400, electrical neuromuscular stimulators, which have been used in multiple previous clinical studies for modulation of pain and have received FDA approval. The (2) electrodes for the device will be placed on the subjects left cervical (neck) region. The stimulator will be placed in a comfortable position, such as next to the pillow. The stimulators are battery-powered and allow configuration of the stimulation parameters to the comfort of the patient. Parents will be trained on where to place electrodes, how to ensure that the electrodes make a good contact with the skin, and how to set the stimulation parameters.

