#### SCHEDULE of Events

STUDY PROCEDURES (*experimental procedure)	Baseline	3 mon	6 mon	9 mon	12 mon	15 mon	18 mon	21 mon	24 mon
Informed consent	x								
Inclusion/exclusion criteria	Х								
Medical history	Х	х	х	х	х	х	х	х	х
*nVNS 2 times daily x 60 mins each (log book maintained and reviewed)	x	x	x	x	x	x	x	x	x
Physical and neurological examination	x		х		х		х		х
Vital Signs	Х		х		х		х		х
Cytokine profile	Х		х		х		х		х
EKG	Х		х		х		х		х
R-ODS scale and handheld dynamometer	х		х		х		х		х
Nerve conduction study	x				х				х
Adverse events	х	х	х	х	х	х	х	х	х
Concomitant medications (IVIG, steroids, PLEX)	х	х	х	х	х	х	х	х	х
Telephone visit/ check (To limit inperson visits due to COVID-19 pandemic)		х		х		х		x	

**Table 1. Study outline for nVNS in CIDP patients.** Patients will be followed for two years with nVNS as an adjunctive to standard IVIG therapy. Patients will be validated against the stated inclusion criteria prior to enrollment in the study. Baseline measurements before nVNS is added will be taken to determine change in physiological and functional outcomes over time. All procedures other than in-home vagus nerve stimulator therapy will take place at CHOA under the direct guidance of the PI. Parents will be trained on where to place electrodes, how to ensure that the electrodes make a good contact with the skin, and how to set the stimulation parameters. Patient is not required to have anyone sit with them during the stimulation procedure. At the end of two years, we will understand the benefits (or not) of nVNS in CIDP and the compliance of nVNS therapies in pediatric patients.

Specific Aim 1: Quantify functional changes in motor nerve conduction studies, hand held grip strength, and Rasch-built Overall Disability Scale (R-ODS) in CIDP patients receiving standard of care treatment and daily nVNS.

• **nVNS Therapy.** The nVNS therapy will be delivered using a handheld electrical neuromuscular stimulator

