CHOA PI: [name] Study Protocol Version: 09/16/2021 (VitalStim 400) device. It is safe, effective at stimulating the vagus nerve, and easy to use by patients outside the clinic. Electrical neuromuscular stimulator devices have been used for years in pain-related preclinical and clinical research. Patients will be requested to deliver nVNS 2 times per day for 60 minutes each time for at least 5 days per week. The stimulation frequency (number of pulses) and amplitude (amount of current) will be set during the initial baseline session in the clinic and will be set to prevent discomfort to the patient or impact cardiorespiratory parameters. Initial stimulation parameters will be guided by previous reports of nVNS in patients. Patients will be trained on all appropriate methods for using the devices and asked to report the number of daily therapy sessions completed. Patients will be asked to continue their standard medication regimens which include in majority of cases 3 weekly IVIG (1 gm/kg) infusions, with or without steroids and plasma exchange.

- Handheld dynamometer: In the pediatric NM clinic we use a Jamar Handheld Dynamometer with reference range (in kilograms and pounds) for children ages 5-18 years. Both right and left hand grip strength would be measured. Best of the three attempts will be used in each hand. We routinely use dynamometer.
- **R-ODS:** Twenty four item motor scale based on day to day activities with a score of 0-48. The scale was designed for adult CIDP subjects however based on our experience in children the scale captures pediatric motor disability as well.
- NCS metrics: Motor nerve conduction studies are well tolerated in children. We routinely study median, ulnar, common fibular and tibial nerves on one side of the body. Distal and F wave latency, conduction velocity and amplitude will be recorded in all nerves. In addition, drop in motor amplitude and or temporal dispersion on proximal stimulation will be noted.

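### Nerve conduction is read by someone who knows the visit, and so the treatment state; a visit-masked re-read by existing staff would cheaply reduce reading bias, provided raw waveforms are saved from the start

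*Combined protocol and SAP*

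**What the plan says.** On who evaluates, section VII (Data Safety) states: "The principal investigator (PI) will perform and supervise all evaluations during the study period". The note to Table 1 in the Schedule of Events adds: "All procedures other than in-home vagus nerve stimulator therapy will take place at CHOA under the direct guidance of the PI".

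On design, the same note says "Patients will be followed for two years with nVNS as an adjunctive to standard IVIG therapy" and "Baseline measurements before nVNS is added will be taken to determine change in physiological and functional outcomes over time". No sham or concurrent control group is described. Section II gives the size: "A total of 15 subjects, from age 5 years to 21 years, will be included in the study".

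On the outcome, motor nerve conduction is listed first in Aim 1. The NCS metrics bullet under Specific Aim 1 names four nerves on one side of the body (median, ulnar, common fibular, tibial) and says "Distal and F wave latency, conduction velocity and amplitude will be recorded in all nerves". It also says that "drop in motor amplitude and or temporal dispersion on proximal stimulation will be noted", with no measurement rule. Table 1 places nerve conduction studies at baseline, 12 and 24 months.

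The hypothesis is directional: nVNS is expected to stop the decline in motor nerve conduction and grip strength. No section provides for masked, independent or central reading. Section III (Risks) lists small sample size, missing natural-history data and compliance as difficulties, but not assessor bias.

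**The concern.** In a single-group study where everyone is treated, the visit label is the treatment label. A reader who knows that a recording is from baseline or month 24 knows whether it precedes or follows nVNS, and knows which result the study hopes to see. Placing a cursor for an onset or F-wave latency involves judgement. Deciding whether temporal dispersion is present involves more, because the plan gives no rule for it.

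R-ODS is a questionnaire on daily activities and grip depends on effort. Nerve conduction is the functional outcome least exposed to the patient's own expectation, so it is worth protecting from the reader's. In a controlled trial with readers masked to arm, a common reading drift would largely cancel between arms. Here it passes unreduced into the change from baseline. Because the claim is that decline is halted, drift could act in two ways: it could create an apparent gain, or it could hide a real decline.

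**Working it through.** The plan states no alpha, power, effect size or SD for nerve conduction, so there is no figure of its own to reproduce. The calculation below shows only how sensitive a test would be to a reading shift.

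**Inputs**
- From the plan: n = 15 (section II); 3 nerve conduction visits (Table 1); 4 nerves and 4 quantities per nerve (NCS metrics bullet).
- Assumed: a two-sided 5% paired t-test on change from baseline; a constant reading shift b toward benefit, in SDs of the within-patient change score.

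**Formula**

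The test statistic follows a noncentral t distribution with n − 1 = 14 degrees of freedom and noncentrality b√n = 3.873b. The critical value is t(0.975, 14) = 2.145. The chance of a falsely favourable significant result is P(T > 2.145).

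**No true change, n = 15**

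| Assumed shift b (SD) | Noncentrality | Significant in favour of nVNS | Significant in either direction |
|---|---|---|---|
| 0 | 0 | 2.5% | 5.0% |
| 0.1 | 0.387 | 5.5% | 6.5% |
| 0.25 | 0.968 | 14.5% | 14.7% |
| 0.5 | 1.936 | 43.8% | 43.8% |

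The favourable column is the relevant one, since the concern is drift toward benefit. With 10 evaluable patients (9 degrees of freedom, critical value 2.262), the favourable figures are 4.7%, 10.6% and 29.3% for the same three shifts.

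**True decline hidden by the shift, n = 15**

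Let the true decline be 0.5 SD (assumed), so the noncentrality in the direction of decline is (0.5 − b)√15.
- b = 0: 1.936, chance of a significant decline 43.8%
- b = 0.2: 1.162, chance 19.0%
- b = 0.3: 0.775, chance 10.8%

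**Workload of a masked re-read**
- Studies: 15 children × 3 visits = 45
- Nerve studies: 45 × 4 = 180
- Values: 180 × 4 = 720, plus proximal amplitude drop and dispersion

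These are upper limits for studies and nerve studies, reached only if all children complete all three visits.

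**The case against.** The strongest reply is that this is a small single-site study of a rare disease, that nothing in the plan is contradicted, and that the proposed masking is weak. Much of that stands.

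- **Masking is partial.** The same reader will usually have seen each tracing on the day, from only 15 children followed in the clinic. Limb distance grows with the child and could reveal visit order. Withholding distances during the re-read deals with the second problem but not the first.
- **Only reading bias is addressed.** Electrode placement, stimulus level and repeat attempts at recording are untouched. So are encouragement in grip testing and expectation in R-ODS.
- **The larger limit is the design.** Without a control group, relapse and remission, growth and changes in co-treatment remain mixed with any nVNS effect. A reader might infer that masked reading would let the study support a claim of halted decline. It would not. Nor does nerve conduction carry that claim alone: the hypothesis names grip strength beside it.
- **The bias sizes are assumed.** Nothing in the documents suggests that cursor placement could shift the mean by 0.5 SD of the change score. At 0.1 SD the favourable error rate rises only from 2.5% to 5.5%.

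Two further inferences go beyond the text. One is that the PI personally makes every reading. The wording covers both performing and supervising, and the plan does not say who places the cursors. This narrows the point without removing it, since no masking is planned for supervised staff either. The other is that stored tracings already exist to be re-read. The plan says that values are recorded and findings noted; it does not say that waveforms are kept. Masked re-reading is therefore possible only if saving them is made a requirement.

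These points limit what the change can achieve. They do not supply a reason for leaving the readings unmasked.

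**Conclusion.** The point holds as a low-severity, low-cost improvement. The plan provides no masking of nerve conduction readings to the visit, the visit discloses the treatment state, and no control arm absorbs a systematic reading shift.

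Its size is unknown. The illustrative range of 5.5% to 43.8% depends on the assumed test, alpha and shifts of 0.1 to 0.5 SD. It must not be read as an estimate of this study's false-positive rate. Drift toward benefit is the direction the hypothesis would lead one to expect; the documents contain no evidence that drift will occur or which way it would go. If masking removed reading bias entirely, the favourable error rate would return to 2.5% under the same assumptions. With the same reader, some smaller reduction is realistic.

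**What to change.** Amend the NCS metrics bullet under Specific Aim 1 as follows.

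1. From the first study onward, save the raw waveforms and the limb distances measured at the visit. This cannot be recovered later if only values are kept.
2. After the last visit, the study coordinator removes ID, date and visit from the recordings and puts them in random order.
3. The existing reader (the PI or supervised staff) re-measures distal, proximal and F-wave latencies, amplitude, proximal amplitude drop and temporal dispersion, using a rule written in advance for the last two.
4. Conduction velocity is computed afterwards from the masked latencies and the stored distances, which the reader does not see.
5. The masked values are the analysis values. Same-day readings remain for care.

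Add a sentence stating that this does not mask recording, grip testing or R-ODS.

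The cost is existing staff time for up to 180 nerve studies and at least 720 values, plus the coordinator's work in preparing the files. No extra assessor, visit or patient procedure is needed.
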